6.1 Demographics and baseline characteristics

Demographics and baseline characteristics will be summarised and listed.

Duration of AD in years will be calculated as (age at Week 0) minus (age at onset of AD).

The table of concomitant medication at baseline will include medication starting before the first dose of IMP which does not end before the first dose of IMP. Also, a table of concomitant medication during the treatment period will be included. Concomitant medication with start date equal to the day of exposure end will be assigned to the safety follow-up period, see Section [6.8.4](#). For handling of incomplete dates, see Section [6.8.3](#).

6.2 Disposition

Subject disposition will be summarised and listed.

Trial ID: LP0162-1343	Date: 15-Jun-2021	Version: 1.0 Page 9 of 22
-----------------------	-------------------	------------------------------

6.3 Treatment compliance

Compliance will be summarised and listed. If a dose is received partly, e.g. only one injection, then this dose is treated as a compliant (non-missed) dose in the summary tables.

In case of permanent discontinuation of IMP, only doses missed before permanent discontinuation of IMP will be included in the summary tables.

6.4 Exposure

The exposure time will be defined as detailed in Section [6.8.2](#). Exposure time will be summarised and listed.

Patient years of exposure (PYE) will be calculated as the difference between the start date and time and the end date and time divided by $60 \times 60 \times 24 \times 365.25$.

6.5 Rescue medication

Rescue treatment will be summarised and listed. Initiation of rescue treatment will be presented using a cumulative proportions plot over time instead of the Kaplan-Meier plot described in the protocol.

The table of rescue medication will include medications taken after the first dose and before the (nominal) Week 16 visit (or before day $7 \times 16 = 112$ after first dose, in case the (nominal) Week 16 visit did not take place).

6.6 Analysis of efficacy

Efficacy will be analysed as described in the clinical trial protocol.

Calculation of Weekly average of pruritus NRS

The weekly average will only be calculated if at least 4 out of the 7 weekly assessment are available and otherwise set to missing. In case of several entries on the same day, the worst observation of that day will be used.

When calculating the baseline value for the weekly average of Worst Daily Pruritus, the daily assessments in the 7 days preceding the randomisation will be used, including the day of randomisation.

For the treatment period, the NRS weekly average for Week 1 will be calculated based on scores recorded on day 1 to day 7 (where day 0 is the day of the first dose). Similarly, for

Trial ID: LP0162-1343	Date: 15-Jun-2021	Version: 1.0 Page 10 of 22
-----------------------	-------------------	-------------------------------

Weeks 2 to Week 15, the weekly average for Week x will be calculated based on scores recorded on day $7*x-6$ to day $7*x$ (where day 0 is the day of first dose).

For Week 16, the weekly average will be calculated based on the scores recorded on the day of the Week 16 visit and the 6 days prior to that day.

Calculation of Weekly average of Eczema-related Sleep NRS

Weekly averages of Eczema-related Sleep NRS will be calculated using the same rules as for the weekly averages of pruritus NRS. As for the Worst Daily Pruritus NRS, in case there are several Eczema-related Sleep NRS assessments at the same date only the worst will be used.

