11.3.4.2 Worst Daily Pruritus numeric rating scale

Subjects will assess their worst itch severity over the past 24 hours using an 11-point NRS (Worst Daily Pruritus NRS) with 0 indicating ‘no itch’ and 10 indicating ‘worst itch imaginable’. Subjects will complete the Worst Daily Pruritus NRS as part of the eDiary each day in the morning from Week -2 until Week 16.

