14.3.6.1 Primary estimand: ‘composite’

The primary estimand for the primary endpoints will be:

- Treatment difference in response rates of IGA 0/1 and EASI75 after 16 weeks achieved without rescue medication, regardless of treatment discontinuation.

The primary estimand assesses the expected difference in response rates (defined as response obtained without initiation of any rescue medication) after 16 weeks, resulting from initiation

of a treatment regimen with tralokinumab+TCS compared to a treatment regimen with placebo+TCS.

Primary analysis for the primary estimand

Data retrieved at Week 16 for subjects who have permanently discontinued IMP prior to Week 16 will be included in the analysis. Subjects who prior to the Week 16 visit have received rescue medication will be considered non-responders, reflecting an assumption that initiation of rescue medication indicates failure of the randomised treatment to achieve response, and that a (possible) observed positive response after initiation of rescue medication is not attributable to the randomised treatment. Missing data for subjects who do not attend the Week 16 visit and where rescue medication has not been used prior to Week 16, will be imputed as non-responders.

The difference in response rates between treatment groups will be calculated by the Mantel-Haenszel method stratified by baseline disease severity (IGA 3 or 4). The treatment difference and the corresponding 95% CI will be presented.

Sensitivity analysis

The purpose of the analysis is to assess the robustness of results of the primary analysis with respect to the retrieved data at Week 16.

All subjects who have permanently discontinued IMP prior to Week 16 will be imputed as non-responders, even if no rescue medication has been used. This is to reflect a situation where retrieved efficacy data and concomitant medications could be registered less accurately for subjects who have discontinued treatment. The same Mantel-Haenszel method as used for the primary analysis will be applied including stratification by baseline disease severity.

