14.3.7 Analysis of key secondary efficacy endpoints

The binary key secondary endpoint, reduction of Worst Daily Pruritus NRS (weekly average) ≥ 4 from baseline to Week 16, will be analysed as described for the primary endpoint EASI75 using both estimands with the modification of the ANCOVA imputation model that reduction of Worst Daily Pruritus NRS weekly average replaces EASI where preceding values are used as covariates.

For the continuous key secondary endpoints, change from baseline to Week 16 in SCORAD and DLQI, 2 estimands addressing different aspects of the trial objectives will be defined:

- Primary estimand: 'composite'.
- Secondary estimand: 'hypothetical'.

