6.8.6 Early termination and unscheduled visits

When no data are available from a certain scheduled post-baseline visit for a subject, data from early termination visits and unscheduled visits have the potential to replace data from that particular scheduled visit in data summaries, provided the data are collected between 6 days before and 7 days after the planned time point for the scheduled visit, as displayed below.

Visit (target day)	Visit window (day is date of assessment minus date of first dose)
Week 2 (Day 14)	Day 8 to 21

Trial ID: LP0162-1343	Date: 15-Jun-2021	Version: 1.0 Page 22 of 22
-----------------------	-------------------	-------------------------------

Week x (Day 7*x) (where x= 4, 6, ..., 16)	Day 7*x-6 to 7*x+7
Safety follow-up	36-49 days after last dose ¹ 106-119 days after first dose ²

1) Subjects who permanently discontinues IMP dosing with last IMP administration <5 weeks before the planned Week 16 visit or complete the treatment period, should have the safety follow-up visit conducted 6 weeks after the last IMP administration.

2) If a subject permanently discontinues IMP dosing with last IMP administration \geq 5 weeks before the planned Week 16 visit, then only the nominal Week 16 visit (16 weeks after randomisation) will be conducted. At this visit, the relevant safety information will be collected.

When both unscheduled and early termination visits exist within the given visit window, the early termination visit will be selected for analysis. When no early termination visit and several unscheduled visits exist within the window, the unscheduled visit closest to the target day will be selected for analysis. If the difference is a tie, the latest unscheduled visit will be selected.

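### SAP 6.6 defines no Week 16 diary average when the Week 16 visit is missed, so a subject with complete itch entries is scored as a pruritus non-responder

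*SAP*

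**What the plan says.** The diary rules are in SAP 6.6. For Weeks 2 to 15, "the weekly average for Week x will be calculated based on scores recorded on day" 7x−6 to 7x, with Day 0 the day of first dose; Week 1 is Days 1 to 7 on the same pattern. Week 16 is different: "For Week 16, the weekly average will be calculated based on the scores recorded on the day of the Week 16 visit" and on the six days before it. One completeness rule covers every week: "The weekly average will only be calculated if at least 4 out of the 7 weekly assessment are available and otherwise set to missing". The sleep diary follows the same rules.

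Protocol 11.3.4.2 has subjects rate itch "each day in the morning from Week -2 until Week 16", so entries do not depend on attending a visit. Protocol Appendix 3D adds that electronic patient-reported data are available as soon as they are entered.

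Under Protocol 14.3.7 the itch responder endpoint "will be analysed as described for the primary endpoint EASI75 using both estimands". The composite rule in Protocol 14.3.6.1 makes non-responders of the following: "Missing data for subjects who do not attend the Week 16 visit and where rescue medication has not been used prior to Week 16".

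Two other SAP sections deal with a missed Week 16 visit. Section 6.5 sets Day 112 as the cut-off for the table of rescue medication "in case the (nominal) Week 16 visit did not take place". Section 6.8.6 says that "data from early termination visits and unscheduled visits have the potential to replace data from that particular scheduled visit in data summaries", within a window around the planned day. It then describes the visit so chosen as the one taken for analysis.

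**The concern.** Every diary week but the last can be computed whether or not the subject comes to the site. The last one, which feeds a key secondary endpoint, cannot. A subject who misses the Week 16 visit but has recorded itch every day of that week has data showing response or non-response. The plan nevertheless leaves the value undefined, and the composite rule turns it into failure. Section 6.5 shows that the SAP authors foresaw a missed Week 16 visit, so the silence in 6.6 looks like an omission rather than a decision.

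The stand-in rule raises a similar question for the primary endpoints. Its wording covers summaries in one sentence and analysis in another, so two programmers could classify the same subject differently. The trial has no formal testing (Protocol 14.3.5). The estimates and their intervals are the result, and they should not depend on such a choice.

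**Working it through.** **Inputs.** Diary weeks, four-of-seven rule: SAP 6.6. Rescue-table cut-off: SAP 6.5. Stand-in window, Days 7x−6 to 7x+7: SAP 6.8.6. About 100 subjects randomised 1:1, so about 50 per arm: Protocol 14.1. A nominal Week 16 visit is taken to count as the Week 16 visit.

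**1. The plan's own figure.** 7 × 16 = 112, as SAP 6.5 states.

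**2. Diary days.** For x = 15 the week is Days 7×15−6 to 7×15, that is 99 to 105. Extending the rule to x = 16 gives Days 106 to 112. These days belong to no earlier week. With no Week 16 visit, entries on them enter no weekly average, even if all seven are present.

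**3. Consequence by analysis,** for a subject with no visit, no rescue and at least four entries on Days 106–112:
- Itch responder, composite: non-responder.
- Itch responder, treatment policy by multiple imputation: imputed, not failed. SAP 6.6.2 drops this analysis for itch if discontinued subjects have no Week 16 diary data, which it considers likely.
- Itch responder, treatment-policy sensitivity analysis: non-responder.
- Itch and sleep change, repeated measures (Protocol 14.3.8): the Week 16 value is missing; earlier weeks still contribute.

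**4. Stand-in visits.** The Week 16 window is 112−6 = 106 to 112+7 = 119. Take a subject with IGA 1 at an unscheduled visit on Day 110, no rescue and no Week 16 visit. If the stand-in enters the responder analysis, this is a responder. If Protocol 14.3.6.1 is applied to non-attendance, it is a non-responder. No section gives precedence.

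**5. Rescue and stand-ins.** Let r be the rescue start day and v the stand-in day; the assessment follows rescue if r < v. Suppose stand-ins are used and the Day 112 table cut-off is borrowed for the endpoint, so that rescue counts only if r < 112.
- Uncounted although before the assessment: r = 112 to 118 with v = 113 to 119, giving 1+2+3+4+5+6+7 = 28 day pairs.
- Counted although not before the assessment: v ≤ r < 112 with v = 106 to 111, giving 6+5+4+3+2+1 = 21 pairs, 6 of them same-day.
- If r < v is the rule, both counts are 0.

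**6. Size.** One subject is 1/50 = 2 percentage points of an arm. For scale, the half-width of the unstratified 95% interval for a difference is 1.96 × √[p₁(1−p₁)/50 + p₂(1−p₂)/50]. At assumed response rates this is 17.5 points (80% v 60%), 18.1 (40% v 25%) and 19.2 (60% v 40%).

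**The case against.** The strongest reply is that the case is rare. Sites must try to reschedule a missed visit (Protocol 10.4), and a late visit may simply be recorded as Week 16. Subjects who stop IMP are asked to attend a nominal Week 16 visit (Protocol 10.3), and SAP 6.6.2 expects them to stop filling in the diary. That leaves mainly subjects on treatment who never attend Week 16 yet keep up the diary. Anchoring the week to the visit is also sensible for those who attend, and counting missing data as failure is a deliberate, conservative choice.

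The rarity stands and limits the size. The visit anchor for attenders stands too. The last argument does not reach this case: the data were collected, and only the definition of the week makes them missing.

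Three stronger readings are tempting but unsupported.
- A reader might infer that the plan lets a rescued subject count as a rescue-free responder. Day 112 in SAP 6.5 is written for a descriptive table. The endpoint rule in Protocol 14.3.6.1 is rescue before the Week 16 visit, and SAP 6.8.7 defers to the protocol. If the stand-in is treated as that visit, or if non-attendance means non-response, the gap is zero. It opens only if stand-ins are used and the table cut-off is also borrowed; neither is stated.
- A reader might see SAP 6.8.6 and Protocol 14.3.6.1 as contradicting each other outright. The protocol imputes missing data, and a stand-in arguably supplies them. This is unclear scope.
- A reader might extend the conflict to SCORAD. Protocol 14.3.7.1 multiply imputes missing Week 16 SCORAD in subjects without rescue, so no non-responder rule is in play there.

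**Conclusion.** The diary gap follows directly from the text. Without a Week 16 visit there is no Week 16 itch or sleep average, however complete the diary. For the itch responder endpoint this means failure in the composite analysis and in the non-responder sensitivity analysis; in the repeated-measures analyses it means only a lost value. The scope of the stand-in rule for IGA 0/1 and EASI75 is a real but secondary ambiguity. The rescue gap is a possible programming outcome on one reading, not a rule of the plan.

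The size is 2 percentage points of an arm per reclassified subject, against interval half-widths of about 17.5 to 19.2 points at the assumed rates. The documents do not say how many subjects will be affected. Multiplying a guessed rate of missed visits by 2 points would overstate the effect. For the diary gap, a subject must miss the visit, have at least four entries in the window and meet the response threshold. The number is likely very small. The reason to act is that collected data for a key secondary endpoint are replaced by failure, and avoiding this costs almost nothing.

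**What to change.** In SAP 6.6, add that if there is no Week 16 visit, the Week 16 itch and sleep averages are calculated from Days 106–112 with the same four-of-seven minimum. Rescue started before Day 112 still makes the subject a non-responder in the composite analysis. Keep the visit-based week for those who attend.

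In SAP 6.8.6, state whether an early termination or unscheduled visit on Days 106–119 enters the IGA 0/1 and EASI75 responder analyses, or whether the subject is imputed as a non-responder under Protocol 14.3.6.1. Either choice is acceptable. If stand-ins are used, judge rescue against the date of the assessment analysed and not against Day 112.

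The cost is about three sentences and no new data. The choice should be made before the randomisation code is broken, as Protocol 14.3.16 requires for finalising the SAP.

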6.6.1 Primary efficacy endpoints

Primary analysis for the secondary estimand

As described in the protocol, imputation of missing data at Week 16 will be done using multiple imputations within 4 groups defined according to treatment group and whether or not subjects have permanently discontinued IMP prior to Week 16 assuming data is missing at random (MAR). Imputation within one or more groups may not be feasible if too few data is available. If this is the case, the primary analysis will not be conducted and will be replaced by the corresponding sensitivity analysis where subjects with missing data will be imputed as non-responders.

6.6.2 Key secondary efficacy endpoints:

Reduction of Worst Daily Pruritus NRS (weekly average) of at least 4 from baseline to Week 16 will be based on subjects in the FAS with a baseline Pruritus NRS weekly average of at least 4.

The binary endpoint is planned to be analysed as described for the primary endpoint EASI75 using the two estimands. It is however expected that subjects will not fill in the eDiary when they have discontinued treatment, and it is considered likely, there will be no nominal Week 16 data available for discontinued subjects. If this is the case, the primary analysis of the secondary estimand ('treatment policy') will not be performed for this endpoint. The corresponding sensitivity analysis for the secondary estimand, analysing subjects with missing Week 16 data as non-responders, while otherwise using observed data for the remaining subjects, will still be conducted.

SCORAD

Trial ID: LP0162-1343	Date: 15-Jun-2021	Version: 1.0 Page 11 of 22
-----------------------	-------------------	-------------------------------

For the calculation of SCORAD, the protocol states that dryness is evaluated on uninvolved areas. This means that if a subject has an extent, i.e. total body surface area (BSA) affected by AD, of 100% then there is no area to score. In the event that dryness is missing and extent is 100% then a dryness score of 0 (none/absent) will be imputed.

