9.4 Background treatment (emollients)

All subjects must use an emollient as a background treatment twice daily (or more, as needed) for at least 14 days before randomisation. The background treatment should preferably be an additive free, basic bland emollient. On days where site visits take place, the subjects should preferably postpone application of emollient to after the end of the visit, since the dryness of the skin must be assessed as part of the efficacy assessments.

On lesional skin, emollients should only be applied at times when TCS is not applied (i.e. emollients and TCS should not be used on the same areas at the same time of the day); on TCS-untreated areas, the emollients may be applied at all times.

The subjects must continue their background emollient treatment throughout the trial (including the safety follow-up period).

It will be recorded in the eCRF if background treatment (emollient) has been used as described since last visit; if not, a reason should be provided.

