11.2.5 Body surface area involvement

The total BSA affected by AD will be assessed by the investigator for each section of the body as component A of SCORAD (Section 11.3.3) and will be reported as a percentage of all major body sections combined. The following body regions will be assessed (brackets show the highest possible score for each region): head and neck (9%), anterior trunk (18%), back (18%), upper limbs (18%), lower limbs (36%), and genitals (1%). The total BSA score will be assessed according to the schedule of procedures in Section 4.

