11.3.3 Scoring Atopic Dermatitis

The SCORAD is a validated tool to evaluate the extent and severity of AD lesions, along with subjective symptoms [\(29\)](#). The maximum total score is 103, with higher values indicating more severe disease. SCORAD will be assessed according to the schedule of trial procedures (Section 4).

The assessment will be based on the condition of the disease at the time of evaluation and not in relation to the condition at a previous visit. Whenever possible, SCORAD should be assessed by the same investigator at each visit to reduce inter-rater variability.

The assessment consists of 3 components: A = extent, B = intensity, and C = subjective symptoms.

Extent (A)

The extent of AD is assessed as a percentage of each defined body area and reported as the sum of all areas (maximum score = 100%).

Intensity (B)

The intensity of 6 specific symptoms of AD (erythema, oedema/papulation, oozing/crusting, excoriation, lichenification, and dryness) is assessed by the investigator on an average representative area using the following scale:

0	=	None/absent
1	=	Mild
2	=	Moderate
3	=	Severe

Note: dryness is evaluated on uninvolved areas.

The sum of intensity score of the 6 symptoms will be reported (maximum score = 18).

Subjective symptoms (C)

A subjective assessment of the average itch and sleeplessness over the last 3 days/nights is recorded for each symptom by the subject on a visual analogue scale, where 0 is no itching (or no trouble sleeping) and 10 is unbearable itching (or lot of trouble sleeping), with a maximum possible score of 20.

The SCORAD is calculated as: A/5+7B/2+C.

The extent and intensity of disease will be reported in the eCRF.

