14.3.7.1 Primary estimand for the continuous key secondary endpoints: 'composite'

The primary estimand for the continuous key secondary endpoints will be:

- Treatment difference in change from baseline to Week 16 in SCORAD and DLQI, respectively, achieved without rescue medication, regardless of discontinuation of IMP.

Primary analysis for the primary estimand - continuous key secondary endpoints

Data retrieved at Week 16 for subjects who have permanently discontinued IMP prior to Week 16 will be included in the analysis. Subjects who prior to the Week 16 visit have received rescue medication will be considered non-responders by using worst observation carried forward (including the baseline value).

Missing Week 16 data among subjects who did not use rescue medication will be imputed using multiple imputations (100 copies of the dataset, seed=16201343) assuming missing at random within arms (based on sequential use of an ANCOVA model for Weeks 2, 4, 6, ... and 16). The stepwise imputation model will be estimated based on available data from all subjects but excluding individual subject data captured after initiation of rescue medication or permanent discontinuation of IMP. For each of the 100 imputed datasets, the continuous secondary endpoint will be analysed using an ANCOVA model with effects of treatment, baseline disease severity (IGA 3 or 4), and baseline value. The estimates and standard errors from the 100 analyses will be combined using Rubin's rule to form a unique point estimate and standard error.

Sensitivity analysis for primary estimand - continuous key secondary endpoints

A tipping point analysis using multiple imputations will be performed with the purpose to assess the robustness of results of the primary analysis for the primary estimand with respect to the missing at random assumption regarding missing Week 16 data. The tipping analysis will assess how severe the departure from the missing at random assumption in the tralokinumab arm must be in order to impact the results.

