6.8.1 Baseline value

Unless otherwise specified, the baseline value is defined as the latest pre-dose assessment.

Missing baseline assessments

When the baseline value is missing, endpoints concerning a change from baseline cannot be derived, and such subjects will be excluded from the analysis. Since the missingness of baseline values are unrelated to the assigned treatment, bias should not be a concern with this approach.

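### Does setting a missing dryness score to 0 at 100% extent distort the SCORAD endpoint?

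*SAP*

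**What the plan says.** Protocol 11.3.3 defines the score: "The SCORAD is calculated as: A/5+7B/2+C". A is extent (0 to 100), B the sum of six signs graded 0 to 3 (maximum 18), and C two symptom scales (maximum 20). It adds: "The maximum total score is 103, with higher values indicating more severe disease". On the sixth sign it says: "Note: dryness is evaluated on uninvolved areas". The protocol has no rule for a subject without uninvolved skin.

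SAP 6.6.2, under SCORAD, fills that gap. It observes that full involvement leaves no skin on which to grade dryness, and continues: "In the event that dryness is missing and extent is 100% then a dryness score of 0 (none/absent) will be imputed". A dryness grade that a site does record at 100% extent is left alone.

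Change in SCORAD to Week 16 is a key secondary endpoint (Protocol section 6, Panel 3). Protocol 14.3.5 plans no formal testing, only estimates with 95% confidence intervals. If SCORAD were left missing at baseline, SAP 6.8.1 would apply: "such subjects will be excluded from the analysis".

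**The concern.** Zero is the best grade, and it goes to subjects with the greatest possible extent. The SAP says why the item can be missing but does not argue for 0 over another value. A fully involved subject can then score below a less involved one whose other items are the same, which seems at odds with a scale on which higher means worse.

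No planned analysis varies the choice. The tipping-point analysis (Protocol 14.3.7.1) and the copy-reference analysis (14.3.7.2) deal with missing visits; both treat a SCORAD completed with dryness 0 as observed. Yet for unreturned TCS tubes SAP 6.6.6 runs two opposite extremes. The protocol also takes trouble over this item: section 9.4 asks subjects to hold back emollient before a visit because "the dryness of the skin must be assessed as part of the efficacy assessments".

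At stake would be a shift of unknown direction in a key secondary estimate. A 0 at Week 16 overstates improvement. A 0 at baseline understates it once dryness can be graded again, and can lower the worst value carried forward after rescue.

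**Working it through.** **Inputs.** Formula, item ranges and maximum: Protocol 11.3.3. Regional shares, which sum to 9 + 18 + 18 + 18 + 36 + 1 = 100: Protocol 11.2.5. About 100 subjects randomised 1:1, so about 50 per arm: Protocol 14.1.

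**1. The plan's own figure.** 100/5 + 7×18/2 + 20 = 20 + 63 + 20 = 103, as stated.

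**2. Ceiling under the rule.** With dryness 0, B is at most 15, giving 20 + 52.5 + 20 = 92.5. At 99% extent with dryness 3: 19.8 + 63 + 20 = 102.8. The contrast is real, but it sets dryness 0 against dryness 3 at the top of the scale. It arises only if every region, including the 1% for genitals, is fully involved and the item is also blank.

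**3. Is the order reversal peculiar to the rule?** With other items equal, a subject with extent x and dryness d outscores one at 100% with dryness set to 0 when x/5 + 3.5d > 20, that is x > 100 - 17.5d: above 82.5%, 65% and 47.5% for d = 1, 2, 3. The same happens wherever dryness is properly recorded as 0. Extent 95% with dryness 0 contributes 19.0; extent 83% with dryness 1 contributes 16.6 + 3.5 = 20.1. A dryness grade is worth 3.5 points and a percentage point of extent 0.2, so totals need not rise with extent when dryness differs. The protocol's statement describes the total score and is not contradicted.

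**4. Size per visit.** One dryness grade moves a visit by 3.5 points, and three grades by 10.5. With 50 per arm, one affected Week 16 visit moves its arm's raw mean by up to 10.5/50 = 0.21 (0.07 per grade). Two more such visits on placebo than on tralokinumab move the raw difference by up to 0.42, toward zero.

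**5. Size over a trial.** The documents give no frequency, so this step rests on assumptions. The simulation used 50 per arm, with these settings:
- 0.5% to 10% of subjects at 100% extent at baseline;
- up to 4% of placebo and 2% of tralokinumab subjects first reaching 100% at Week 16;
- rescue in 10% and 3% of placebo and tralokinumab subjects, with worst observation carried forward;
- mean improvement 38% and 55% on placebo and tralokinumab;
- ANCOVA on treatment, baseline IGA and baseline score.

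The adjusted difference under the rule, minus that under an assumed dryness grade (positive = toward zero, against tralokinumab), was:
- nobody first reaching 100% at Week 16: 0 to +0.36 (0 to +0.01 at 0.5% prevalence);
- all settings: -0.18 to +0.61.

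The simulated 95% CI half-width was 7.0, so the largest effect is 0.61/7.0, about 9%. By step 4, moving the raw difference by one half-width would take 7.0/0.21, about 33 more affected visits in one arm than in the other, each three grades off.

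**6. Is the obvious alternative better?** Pro-rating sets B to 6/5 of the sum S of the other five signs. The result minus that under the assumed dryness was:

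| Assumed dryness | Current rule | Pro-rating |
|---|---|---|
| 0-1 | -0.04 to +0.12 | -0.40 to +0.13 |
| 0-3 | -0.10 to +0.35 | -0.16 to +0.06 |
| 2-3 | -0.18 to +0.61 | -0.01 to +0.06 |

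Pro-rating is closer if dryness would have been high and worse if low, where its -0.40 favours tralokinumab. Reversals also remain, when x > 100 - 17.5(d - S/5). At S = 12 that means d = 3 above 89.5%. At S = 6 it means d = 2 above 86% and d = 3 above 68.5%.

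**The case for a change.** The best case against the rule is that an undefined item still needs a stated reason or a pair of bounds, and the SAP gives neither. Part of this stands: the text moves from there being no skin to grade straight to 0 without defending the value, and no planned output shows how many visits are affected. A count by arm and a repeat run with dryness 3 would be cheap and informative.

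They are additions, however, not repairs. The value follows readily from the scale, on which 0 means none or absent. The tube comparison is weak: an unreturned tube has a real weight that nobody knows, whereas here no true grade exists, so runs at 0 and 3 would show sensitivity without bracketing a truth. Pro-rating as the main score would assume that dryness of absent skin tracks five signs graded on a representative area, which neither document supports. It would also change the scoring in a trial designed to judge similarity with LP0162-1339 (Protocol 12.1 and 14.1), whose convention for this case the documents do not give.

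Some rule is needed in any case. Without one, subjects at 100% extent with dryness blank at baseline would drop out of the change analysis.

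**Conclusion.** The concern does not hold. The SAP fixes a convention, before unblinding and identically for both arms, for an item that cannot be graded when no uninvolved skin remains. The scale arithmetic behind the concern is correct, but it shows a property of SCORAD's weights, not an error in the rule.

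The effect is at most 0.21 points on an arm mean per affected Week 16 visit. In the simulated settings it was -0.18 to +0.61 on the treatment difference, and never in tralokinumab's favour unless some subjects first reach 100% extent at Week 16. These are ranges over assumed frequencies, dryness grades, rescue rates and improvements, not limits. Multiple imputation and the repeated-measures analysis were not simulated. With no formal testing, and with IGA and EASI unaffected, following the plan as written gives a sound SCORAD result.
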